- Patient evaluation of the overall treatment (PGI) using a 5-point Likert scale will be conducted at 6 week, 3 month and 6 month follow-up visits.
- After each treatment, the PI or co-investigator will be asked to evaluate the ease of treatment using a 5-point Likert scale.
- After each treatment, the subject will be asked the degree of discomfort experienced as a result of treatment using a 5-point Likert scale.
- Events will be evaluated and recorded.

Questionnaires and evaluations

Questionnaires will be administered by a **research nurse coordinator who is blinded to the patient's therapy**. Sexual function, GSM, and urinary function will be evaluated with the 10-cm VAS, Female Sexual Function Index (FSFI), Day-to-day Impact of Vaginal Aging (DIVA), and Urogenital Distress Inventory (UDI-6), both at baseline prior to 1st laser treatment or commencing with vaginal estrogen (depending on treatment group), and at 12 weeks from

baseline (+/- 1 week) but prior to 3rd laser treatment (if applicable), and at 3 months follow-up after 3rd laser treatment (if applicable). Note that all patients will follow up 6 months from baseline visit for final assessment

The DIVA questionnaire will be administered at baseline, 3 month, and 6 month follow-up visit period, in addition to the FSFI, UDI-6, VHI, and PGI during final assessment. All questionnaires are supplied in the appendix.

Calendar of Study Procedures

	Baseline	6 weeks	3 months	6 months
Informed Consent	X			
H & P	X			
MonaLisa Touch vaginal laser ¹	X	X	X	
Vaginal estrogen therapy ^{2, 3, 4}	X	X	X	
Vaginal symptom VAS	X	X	X	X
Vaginal health index VHI	X	X	X	X
Vaginal maturation index	X			X
DIVA questionnaire	X		X	X
Vagina dilator calibration	X	X	X	X
FSFI	X		X	X
UDI-6	X		X	X
Likert scale (laser patient)	X	X	X	
PGI		X	X	X
Likert scale (laser provider ease)	X	X	X	
Adverse events	X	X	X	X
Sexual activity	X	X	X	X

¹A treatment cycle includes three laser applications (every 5-7 weeks).

²Conjugated estrogen cream (Premarin[®]): 0.5g of cream intravaginally daily (using applicator or fingertip) for two weeks (fourteen days) then 0.5 g twice weekly for 24 ± 2 additional weeks, **or**

³Estradiol cream (ESTRACE[®]): 1.0 g of cream intravaginally daily (using applicator or fingertip) for two weeks (fourteen days) then 1.0 g twice weekly for 24 + 2 additional weeks, **or**

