All study data will be transferred and managed electronically using REDCap (Research Electronic Data Capture). Each subject will be entered into REDCap using the assigned identification number from the master excel file. REDCap is a secure, web-based application designed to support data capture for research studies, providing user-friendly web-based case report forms, real-time data entry validation, audit trails, and a de-identified data export mechanism to common statistical packages. The system was developed by a multi-institutional consortium which was initiated at Vanderbilt University and includes the Cleveland Clinic. The

database is hosted at the Cleveland Clinic Research Datacenter in the JJN basement and is managed by the Quantitative Health Sciences Department. The system is protected by a login and Secure Sockets Layers (SSL) encryption. Data collection is customized for each study as based on a study-specific data dictionary defined by the research team with guidance from the REDCap administrator in Quantitative Health Sciences at the Cleveland Clinic.

Statistical Analysis Plan

Sample Size Rationale

We plan to enroll and randomize 196 patients in this non-inferiority trial comparing vaginal estrogen therapy to laser treatment of vaginal atrophy. The primary outcome will be subjective assessment of vaginal dryness as assessed by 10 cm visual analog scale at 6 months after initiating treatment. Assuming an alpha of 0.025 and a standard deviation of 2.0 [24], 85 subjects in each group will provide a 90% power to reject the null hypothesis (H0) that the true difference in vaginal dryness VAS score (Vaginal Estrogen – Vaginal Laser) is less than or equal to 1.0 cm on the VAS (effect size 0.5) in favor of the alternative hypothesis (H1): the true difference is greater than 1.0 cm using a one sided two sample t-test. Anticipating a 15% loss to follow-up and/or drop-rate over the period of the study, the total enrollment goal is 196 participants.

Analysis Plan

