This study is a non-inferiority study design. The predefined non-inferiority margin is a difference of 1.0cm on a 10cm VAS. To minimize bias towards a finding of non-inferiority, data from women who were eligible and received the assigned treatment (per protocol) will be used for the analysis of the primary outcome. The primary outcome will be presented as the difference in VAS scores between treatments (Vaginal Estrogen – Vaginal Laser). The hypothesis of non-inferiority of the two treatment groups will be tested by comparing the lower limit of the two-sided 95% confidence interval (equivalent of a one-sided significance level of 0.025%) of the absolute difference with the margin set at -1.0cm. A secondary analysis of the primary outcome according to original treatment assignment (intent to treat) will also be performed as well as standard superiority testing using Student's t-test. If differences in baseline patient characteristics are noted, linear regression analysis adjusting for these differences will also be performed. Secondary outcomes will be analyzed using the intent to treat population using Pearson's Chi-square test for categorical data, Student's t-test for parametric continuous data, or Wilcoxon rank sum test for ordinal or nonparametric continuous data. Changes in patient reported outcome questionnaires (FSFI, DIVA, UDI-6, etc.) will be compared between treatments using repeated measures ANCOVA.

SAFETY AND ADVERSE EVENTS

Definitions

Adverse events include prolonged vaginal bleeding beyond 48 hours, heavy vaginal bleeding, bothersome vaginal irritation, bacterial vaginosis, vaginal yeast infection, post-procedural fever, and skin burn.

Recording of Adverse Events

At each contact with the subject, the investigator will seek information on adverse events by specific questioning and, as appropriate, by examination. Information on all adverse events will be recorded immediately in the source document, and also in the appropriate adverse event section of the case report form (CRF). All clearly related signs, symptoms, and abnormal diagnostic procedures results will also be recorded in the source document.

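### The plan gives no rule for a missing 6-month dryness VAS in either non-inferiority analysis, so by default the intent-to-treat check would not test for bias from missing outcomes

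*Combined protocol and SAP*

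**What the plan says.** The Analysis Plan states that "This study is a non-inferiority study design" and that "The predefined non-inferiority margin is a difference of 1.0cm on a 10cm VAS". The effect is the estrogen minus laser difference in dryness VAS, and the Sample Size Rationale sets the time point at 6 months. Non-inferiority is judged by "comparing the lower limit of the two-sided 95% confidence interval" against -1.0 cm.

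The primary set is per protocol: eligible women who received their assigned treatment. The plan chooses it expressly to limit bias towards non-inferiority. It then adds: "A secondary analysis of the primary outcome according to original treatment assignment (intent to treat) will also be performed". Student's t-test is named for superiority, and linear regression is planned if baseline characteristics differ.

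The Sample Size Rationale is the only place that deals with attrition: "Anticipating a 15% loss to follow-up and/or drop-rate over the period of the study, the total enrollment goal is 196 participants". No imputation rule, likelihood-based model or sensitivity analysis is given for a missing 6-month VAS. The only missing-data instruction in the document is item-level scoring of the UDI-6 in the appendix.

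The Calendar of Study Procedures has a row "Vaginal symptom VAS" marked at baseline, 6 weeks, 3 months and 6 months. The Questionnaires and evaluations text lists the 10-cm VAS at baseline, 12 weeks and the final follow-up, with no 6-week assessment. Repeated measures ANCOVA is planned for changes in the patient-reported questionnaires. The FSFI, DIVA and UDI-6 are named there as examples; the VAS is not.

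**The concern.** A confidence interval for a two-group difference, a t-test and a linear regression all work on women who have the outcome. Without a further rule, running them by original assignment drops every woman who lacks a 6-month VAS, including those with 6-week and 3-month scores.

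The intent-to-treat analysis is the plan's only cross-check on the per-protocol result. If both use observed 6-month values, both are open to the same selection by missing outcome, and agreement between them says nothing about that selection.

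Loss could plausibly differ by arm in amount or kind. One arm has three procedure visits, and the case report form records inability to complete the procedure because of discomfort or a constricted vagina. The other arm self-administers drug for about six months, and the background section cites estrogen compliance of 52-74%. If women who fare badly on laser are the ones missing, the observed difference moves towards zero and the 2.5% error rate is not held. If the handling is left open, it could also be chosen after the results are seen.

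**Working it through.** **Reproducing the plan's figures.** The plan says: "Assuming an alpha of 0.025 and a standard deviation of 2.0 [24], 85 subjects in each group will provide a 90% power". With margin 1.0 cm, SD 2.0 and true difference 0:

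- n per arm = 2 × 2.0² × (1.960 + 1.282)² / 1.0² = 84.1, rounded up to 85. Exact t-test power at 85 per arm is 90.0%.
- 170 × 1.15 = 195.5, which gives the stated 196. Dividing instead, 170 / 0.85 = 200, a small difference.
- 15% of 196 is 29.4. That leaves 166.6 women, about 83 per arm, and power of 89.3%. The expected loss is therefore a question of bias, not of power.

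**Bias from using observed values only.** Let m be the share missing in an arm, and g the amount by which the missing women's unseen 6-month VAS is worse (higher) than that of completers in the same arm. The completer mean is the full-arm mean minus m × g, so for estrogen minus laser:

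observed difference = true difference + m(laser) × g(laser) − m(estrogen) × g(estrogen)

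A positive bias favours laser.

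**One-sided error at a true difference of -1.0 cm.** The standard error with 83 per arm is 2.0 × √(2/83) = 0.310 cm. The error is approximately Φ(bias / 0.310 − 1.96). The table uses the noncentral t. The values of m and g are assumptions; the document gives neither by arm.

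| Missing, laser / estrogen | Gap g, laser / estrogen (cm) | Bias (cm) | One-sided error |
|---|---|---|---|
| 15% / 15% | equal, 0 to 3 | 0 | 2.5% |
| 15% / 15% | 1 / 0 | +0.15 | 6.9% |
| 15% / 15% | 2 / 0 | +0.30 | 15.9% |
| 15% / 15% | 3 / 0 | +0.45 | 30.2% |
| 20% / 10% | 1 / 1 | +0.10 | 5.1% |
| 20% / 10% | 2 / 2 | +0.20 | 9.3% |
| 20% / 10% | 3 / 3 | +0.30 | 15.8% |
| 10% / 20% | 1 / 1 | -0.10 | 1.1% |
| 10% / 20% | 2 / 2 | -0.20 | 0.5% |
| 10% / 20% | 3 / 3 | -0.30 | 0.2% |

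The normal approximation for the three laser-only rows gives 7.0%, 16.0% and 30.5%.

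**How far a sensitivity analysis must reach.** With 83 per arm the 95% half-width is 1.975 × 0.310 = 0.61 cm. Suppose completers show no difference, 15% of the laser arm is missing and the estrogen arm has no gap. The lower limit reaches -1.0 when 0.15 × g = 1.0 − 0.613 = 0.387, that is, g = 2.6 cm. This is approximate, since it keeps the completer standard error. Shifts that stop at 2 cm would not tip the conclusion in that case.

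**The case against.** A reader might infer that the plan restricts its intent-to-treat analysis to completers. It does not say so: the sentence refers only to original assignment, and the plan is silent on missing values. The observed-case reading follows from the methods named, not from a stated rule. It is also possible that the open-ended list of questionnaires for repeated measures ANCOVA was meant to include the VAS. Even so, that sentence concerns changes in questionnaires and sets no test against -1.0 cm.

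A reader might also infer that the intent-to-treat analysis can check nothing. That goes too far. The per-protocol set is defined by eligibility and treatment received, not by completion. An observed-case intent-to-treat analysis brings back ineligible women and women not treated as assigned, provided they have a 6-month VAS, so it still tests those exclusions. What it cannot test is the effect of missing outcomes.

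Nor does the plan predict 29 missing values. Its wording is "Anticipating a 15% loss to follow-up and/or drop-rate over the period of the study", which can include women who stop treatment, and all women are to attend at 6 months. Twenty-nine is an upper planning figure.

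Finally, the direction is not known. The error rates of 7% to 30% need laser dropouts to do worse while estrogen dropouts show no gap, and a 3 cm gap is 1.5 SD. The cited estrogen compliance makes heavier estrogen loss at least as plausible, and under the pattern shown that is conservative. On the other side, entry requires a VAS of at least 7 cm, so a woman who leaves without benefit could lie well above improved completers.

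These objections limit the claim. They do not supply the missing rule.

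**Conclusion.** The point holds as a gap in both non-inferiority analyses. Handling of a missing 6-month VAS is unspecified, the named methods default to observed values, and on that default the intent-to-treat analysis is no check on bias from missing outcomes and the earlier VAS scores are not used.

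The size depends on assumed loss patterns: no inflation when loss and gap match across arms, about 7% to 30% when only laser dropouts fare worse by 1 to 3 cm, and 1.1% to 0.2% when estrogen loss is heavier with the same gap in both arms. The document does not support saying that the trial will favour non-inferiority, only that it could and that the plan has no means of showing whether it does.

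The intent-to-treat analysis is secondary, and the main decision rests on the per-protocol set, where the same rule is missing. The change should be made, because it is cheap and affects how far a finding of non-inferiority can be trusted.

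**What to change.** - **Model.** Run the intent-to-treat non-inferiority analysis as a mixed model for repeated measures on the dryness VAS of all randomized women (baseline, 6 weeks, 3 months, 6 months), with arm, visit and arm-by-visit. Compare the 95% confidence interval for the 6-month contrast with -1.0 cm.
- **Primary set.** Apply the same model to the per-protocol set, so that the primary decision is covered too.
- **Sensitivity.** Add a delta-adjusted tipping-point analysis. Vary the shift applied to missing 6-month values separately in each arm, extend it until the conclusion changes and to at least 3 cm, and report it beside the main result.
- **Schedule.** Reconcile the Questionnaires and evaluations text, which has no 6-week VAS, with the Calendar of Study Procedures, which does.

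The cost is SAP wording and a little programming. On the calendar's schedule no new visits, data or participants are needed. The downside is that the mixed model relies on data being missing at random; the tipping-point analysis tests how far the conclusion depends on that.

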This is a multi-centered, randomized prospective single blinded clinical trial comparing CO2 fractionated vaginal laser therapy and vaginal estrogen therapy in the treatment of vulvovaginal atrophy/GSM

Study Outcomes:

The primary outcome is subjective improvement of vaginal dryness using a 10 cm Visual analog scale.

The secondary outcomes that will be assessed include

1. An objective evaluation of vaginal atrophy/estrogenization measured by the globally validated “Vaginal Health Index” (VHI) score [reference Bachmann Maturitas 1995 attached]
2. The effect of GSM symptoms on QoL using the DIVA questionnaire [28]
3. The effect of treatment on the vaginal maturation index, at baseline and 6 month follow up
4. The effect of treatment on vaginal wall elasticity, using standard vaginal dilators to determine vaginal caliber
5. The effect of treatment on the female sexual function, by means of the Female Sexual Function Index (FSFI)[29]
6. Calculation of the percentage of patients who are sexually active or resume intercourse after therapy. A sexual function question not included in FSFI has been added to evaluate this.
7. The effect of the treatment on urinary symptoms by means of the Urogenital Distress Inventory (UDI-6) [30]
8. The degree of difficulty encountered by the physician in performing the MonaLisa laser treatment assessed via a 5-point Likert scale,
9. The rate of satisfaction of patients with treatment assessed by the Patient Global Impression of Improvement (PGI), using a 5-point Likert scale.

Subject SelectionInclusion Criteria

- Menopausal with absence of menstruation for at least 12 months
- Presence of vaginal atrophy symptoms [subjective assessment of vaginal dryness ≥ 7 cm on VAS)
- Prolapse stage \leq II, according to the pelvic organ prolapse quantification (POP-Q) system[31]
- No pelvic surgery within 6 months prior to treatment (vulva biopsy may be included after 2 weeks)
- Understanding and acceptance of the obligation to return for all scheduled follow-up visits

- English speaking and able to give informed consent

Exclusion Criteria

- Personal history of vulvovaginal condyloma, vaginal intraepithelial neoplasia (VAIN), vaginal carcinoma, lichen sclerosis, lichen planus, history of vaginal radiation, history of cervical cancer, other gynecologic cancer, or pelvic radiation
- Acute or recurrent urinary tract infection (UTI), or genital infection (e.g. bacterial; vaginosis, herpes genitalis, candida).

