⁴Estradiol vaginal tablet (Vagifem[®]): one tablet (10 microgram) inserted daily into the vagina for two weeks (fourteen days) then 1 tablet inserted intravaginally twice weekly for 24 + 2 additional weeks.

Data Collection & Management:

Baseline data will include the following:

- Patient age, race, vaginal parity, menopausal state, BMI, history of previous use of vaginal estrogen
- FSFI, DIVA, and UDI-6 questionnaires
- VAS for GSM symptoms and VHI for objective GSM findings

Data points recorded during the procedure will include:

- Likert Scales for physician assessment of patient comfort during the procedure.
- Adverse events including inability to complete the procedure due to discomfort or constricted vagina

Post-procedure data will include the following:

- The rate of satisfaction of patients with treatment by mean of the Patient Global Impression of Improvement (PGI), using a 5-point Likert scale.
- The degree of difficulty encountered by the physician in performing the treatment, by mean of a 5-point Likert scale.
- Additionally, untoward side effects of treatment such as new bothersome vaginal irritation and significant vaginal bleeding will be recorded.

Protection of each subject's personal health information will be a priority in this study. One master Excel file containing subject personal information including name and medical record number will be kept in a password-protected file, on a designated protected research drive on a password-protected computer in a locked office at each respective institution. In that file, each subject will be assigned a subject identification number that will be used for the purposes of data collection in order to de-identify subjects.

All paper forms used for data collection will be kept in a research cabinet dedicated to this project, which will be locked at all times, in a locked office at the Cleveland Clinic (or other institution). All forms will contain de-identified information. Identification numbers will correspond to the subjects listed in the master excel file.

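### The non-inferiority test leaves out baseline dryness VAS, although every woman has one; a prespecified baseline-adjusted ANCOVA would be a modest improvement at almost no cost

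*Combined protocol and SAP*

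**What the plan says.** - **Test used for sizing.** The Sample Size Rationale takes as endpoint "subjective assessment of vaginal dryness as assessed by 10 cm visual analog scale at 6 months after initiating treatment" and sizes the trial "using a one sided two sample t-test", with SD 2.0 and 85 women per group for 90% power. It names no covariate and gives no baseline-to-6-month correlation.
- **Deciding analysis.** Under Analysis Plan, "data from women who were eligible and received the assigned treatment (per protocol) will be used for the analysis of the primary outcome". The lower limit of the two-sided 95% interval for Estrogen minus Laser is compared with -1.0 cm, again with no baseline term.
- **Adjustment.** The same section adds: "If differences in baseline patient characteristics are noted, linear regression analysis adjusting for these differences will also be performed".
- **ANCOVA elsewhere.** A repeated measures ANCOVA is planned for changes in the patient-reported questionnaires (FSFI, DIVA, UDI-6 and an open-ended remainder). It is not the analysis compared with the margin.
- **Availability of baseline.** The Inclusion Criteria require "subjective assessment of vaginal dryness ≥ 7 cm on VAS". The baseline list under Data Collection & Management includes "VAS for GSM symptoms and VHI for objective GSM findings", and the Calendar of Study Procedures shows the VAS at baseline.
- **Wording of the endpoint.** Study Outcomes says "The primary outcome is subjective improvement of vaginal dryness using a 10 cm Visual analog scale", which could be read as change from baseline. The Sample Size Rationale and Analysis Plan describe a score.

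**The concern.** Baseline dryness is measured on the primary scale in every woman, yet it plays no part in the interval that decides the trial. A prespecified baseline term would usually narrow that interval and would remove the part of the between-arm difference due to unequal starting severity.

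Two features of the plan add to the case.

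- **The regression rule depends on the data.** It is triggered by differences someone notices, with no rule for what counts and no list of covariates. Nothing says which result governs if the adjusted and unadjusted limits fall on opposite sides of -1.0 cm.
- **The primary set is per-protocol.** The unadjusted interval allows, on average, for chance imbalance between randomised arms. It does not allow for systematic imbalance created by exclusions after randomisation.

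**Working it through.** **Inputs from the documents:** SD 2.0 cm, margin 1.0 cm, one-sided alpha 0.025, 85 per arm. A true difference of 0 is implied but not stated.

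**Assumptions, because the documents give no figures:** baseline uniform on 7 to 10 cm, so its SD is 3/√12 = 0.866; slope *b* of the 6-month score on baseline from 0.3 to 1.0.

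**The plan's own figure.** The normal approximation gives n = 2 × [2.0 × (1.960 + 1.282)/1.0]² = 84.06, which rounds up to 85 per arm. By non-central t with 168 df, power at 85 per arm is 90.0%. The stated figure reproduces without adjustment.

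**Effect of the baseline term.** Correlation r = *b* × 0.866/2.0. Residual SD = 2.0 × √(1 − r²). Half-width = t × residual SD × √(2/85), with 167 df. Equivalent extra women per arm = 85/(1 − r²) − 85.

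| Slope *b* | r | Residual SD | Power | 95% half-width (cm) | Equivalent extra per arm |
|---|---|---|---|---|---|
| unadjusted | – | 2.000 | 90.0% | 0.606 | – |
| 0.3 | 0.130 | 1.983 | 90.5% | 0.600 | 1.5 |
| 0.5 | 0.217 | 1.953 | 91.3% | 0.591 | 4.2 |
| 0.7 | 0.303 | 1.906 | 92.5% | 0.577 | 8.6 |
| 1.0 | 0.433 | 1.803 | 94.9% | 0.546 | 19.6 |

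If the baseline SD is 0.6 to 1.0 instead, r runs from 0.09 (0.3 × 0.6/2) to 0.50 (1.0 × 1.0/2). These figures charge one degree of freedom for the covariate. Chance baseline imbalance also inflates the adjusted variance by about 1/(170 − 4) = 0.6% on average, which takes roughly 0.1 to 0.2 points off each adjusted power.

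**Attrition.** If 15% of 196 are lost, 166.6 remain, about 83 per arm. Unadjusted power is then 89.3%. Adjustment gives 89.8%, 90.7% and 91.9% at slopes 0.3, 0.5 and 0.7.

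**Effect of imbalance.** The SE of the baseline difference is 0.866 × √(2/85) = 0.133 cm. The unadjusted estimate shifts by *b* times the imbalance: 0.04 to 0.13 cm at 1 SE and 0.08 to 0.27 cm at 2 SE.

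Set the true difference at -1.0. Non-inferiority is then declared if the estimate exceeds -1 + 0.606. Given an imbalance of k SE, the estimate is normal with mean -1 + *b* × k × 0.133 and SD equal to the residual SD × √(2/85). The conditional chances of a false declaration across slopes 0.3 to 1.0 are:

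- baseline higher in the estrogen arm: 3.1% to 4.4% at 1 SE; 4.2% to about 11% at 2 SE;
- baseline higher in the laser arm: 1.7% down to 0.4% at 1 SE; 1.2% down to 0.1% at 2 SE.

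Over all randomisations these average 2.5%.

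**The case against.** The strongest reply is that nothing is broken. The unadjusted test is valid under randomisation, its power is as stated, and at slopes of 0.3 to 0.5 the gain is only 0.5 to 1.3 power points and about 0.005 to 0.014 cm of half-width, against a 1.0 cm margin. The 7 cm entry threshold restricts the baseline range and so caps the gain. The larger figures (94.9% power, 20 women per arm, 11% conditional error) all need a slope of 1.0. This stands: the gain is modest and no large one should be promised.

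The conditional errors are not a type I error problem. They are offset by the mirror cases, and a 2-SE imbalance in the harmful direction has about 2.3% probability under randomisation. That also stands.

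The endpoint could instead be change from baseline, with 2.0 as the SD of change. Baseline would then already enter the primary analysis, and the gains reverse in order: 92.5%, 91.3%, 90.5% and 90.0% at slopes 0.3, 0.5, 0.7 and 1.0. This affects the size and not the recommendation. With baseline as a covariate the treatment estimate is the same under either reading, and the worst case loses essentially no power. A plain change score is no substitute: if 2.0 is the SD of the 6-month score, the SD of change is 2.07 at slope 0.3 and 2.00 at slope 0.5.

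The plan also allows regression for noted differences, and the VAS might be covered by the open-ended questionnaire list. Neither route decides non-inferiority.

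Finally, adjusting for baseline VAS removes only the linear imbalance in that covariate, not selection into the per-protocol set generally. The size of any per-protocol imbalance cannot be worked out from the documents.

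**Conclusion.** The point holds as an improvement and not as an error. The deciding comparison omits a covariate measured on every woman, and the only adjustment offered is supplementary and defined after the fact.

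If 2.0 is the SD of the 6-month score and baseline is uniform on 7 to 10 cm, slopes of 0.3 to 0.7 bring power from 90.0% to 90.5-92.5%, equivalent to about 2 to 9 more women per arm. A slope of 1.0 is the upper end, at 94.9% and about 20 per arm. The slope and the baseline SD are assumptions.

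The case for acting rests on three things together: a small gain in precision, removal of linear baseline imbalance in a set that randomisation no longer protects, and one fixed deciding analysis in place of a data-dependent one. The change is worth making because it costs so little. The existing sample size does not depend on it.

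**What to change.** In the Analysis Plan, before outcome data are examined:

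- Define the primary model as an ANCOVA of 6-month dryness VAS on treatment, with baseline dryness VAS as a prespecified covariate. Compare the lower limit of its two-sided 95% interval for Estrogen minus Laser with -1.0 cm.
- State that this interval decides non-inferiority.
- Use the same model for the intention-to-treat analysis of the primary outcome.
- Keep the unadjusted t-test, and any regression prompted by observed imbalance, as labelled sensitivity analyses.

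The margin, alpha and sample size stay as they are. The cost is SAP wording and one degree of freedom, with no new data, visits or participants.
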